### Hypersensitivity Events of Special Interest

In October 2021, we were informed of 3 participants who experienced hypersensitivity reactions in a Molecular Partners study of 20 healthy volunteers. The 3 participants received a 400 mg subcutaneous dose of MP0420 and each developed non-serious (mild to moderate) rash and joint/body pain 10 to 20 days after the single subcutaneous infusion. A total of 8 participants received the 400 mg dose in this study.

These cases were discussed on October 20, 2021, at a TICO investigator meeting and are also described in a memorandum from trial leadership to investigators in ACTIV-3 (TICO) on November 2, 2021. At that time we requested that investigators increase vigilance of participants who developed rash and simultaneously joint, muscle, and/or body aches.

On November 5, 2021, revised informed consents and drug information sheets that described these events were sent to sites and to the Advarra central IRB.

On December 7, 2021, all participants for whom rash adverse events had been reported through Day 28 were identified. Sites were asked to complete an eCRF for each event. Eleven participants experienced rash events through Day 28. The number and percentage of participants with a rash event by treatment group will be summarized. Rash events associated with myalgia, arthralgia, or generalized aches and pains will also be summarized by treatment group.

Line listing of events will include severity grade, rash characteristics, location, and other solicited events that occurred simultaneously.

No formal statistical testing will be carried out on the rash events alone. In a supplemental analysis for the Day 28 composite safety outcome which includes deaths, SAEs, organ failure, serious infection and grade 3 or 4 adverse events, the rash adverse events will be included as a separate component.

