- AEs, SAEs, and UPs will be classified by MedDRA® system organ class. AEs will be graded for severity according to the *DAIDS AE Grading Table*. Grade 1-4 clinical AEs will be reported at baseline (Day 0 prior to infusion of the investigational agent), Day 0 after the infusion, Days 1-7, and on Days 14 and 28.

The number and percent of participants with AEs will be summarized by day (Day 0 separately prior and after the infusion) and grade, and by system organ class and grade. Comparisons between treatment groups will be for the proportion of participants with AEs of a given grade or higher (i.e., any grade, grade 2+, grade 3+, grade 4). The treatment comparisons will be performed using stratified CMH tests or logistic regression.

- For comparisons by day, the proportion of participants with any grade AEs will be compared for Days 0 (after infusion) through 7, and on Days 14 and 28.
- For comparisons by grade, the proportion of participants who experienced any grade AEs (grade 2+ AEs, etc.) between Day 0 (after the infusion) through Day 7 will be compared.
- For the comparison by system organ class, CMH tests will be performed if the number of participants with AEs is sufficiently large. System organ classes may be split up into MedDRA® preferred terms (PT) for system organ classes where the treatment difference is significant.

Other clinically meaningful AE groupings (beyond system organ class) may be developed by the study team, who are blinded to the treatment effect.

- In addition to any grade AEs through Day 7, grade 3 and 4 clinical AEs are being reported through Day 28. The number and percent of participants with incident grade 3 or 4 AEs through Day 28 will be summarized, overall and by system organ class, and compared between treatment groups using stratified CMH tests. (A grade 3 or 4 AE is considered “incident” if the event was not present at baseline or increased to grade 3 or 4 from grades 1 or 2.)

To illustrate the time course, the incidence of *grade 3 or 4 AEs or death* through Day 28 will be summarized by treatment group using Kaplan-Meier estimates of the cumulative incidence functions (CIF).

- Infusion-related reactions and symptoms during infusion or within 2 hours after infusion of the investigational agent or placebo, and infusion cessation prior to completion will be tabulated and compared between treatment groups; analyses are described in section 6.

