## Appendix C. Safety Data Collection

**Table C-1. Overview of Safety Data Collection** (protocol version 3, section 10).\*

	Infusion +2 hrs	Days 0-7	Day 14	Day 28	Day 90	Months 6, 12, and 18
Infusion-related reactions and symptoms	X					
Clinical AEs of any grade severity		X	X	X		
Grade 3 and 4 clinical AEs from Day 7 through Day 28 			X	X		
Targeted laboratory abnormalities of any grade		X (Day 5)				
Hospital admissions and deaths		Collected through Month 18				
Targeted clinical events collected as study endpoints 	Collected through Day 90					
SAEs not exempt from reporting (i.e., not considered a protocol specified exempt event) 	Collected through Day 90					
Any SAE related to study intervention	Collected through Day 90					
Unanticipated problems	Collected through Day 90					

 Grade 3 and 4 clinical AEs on Days 1-7 are reported each day; those occurring between Days 8 and 14 are reported at the Day 14 visit, and those occurring between Days 15 and 28 are reported at the Day 28 visit.

 Protocol-specified exempt serious events (PSEE); these events are listed below. See section 10.2.5 of the TICO study protocol and the PIM for information on PSEE.

\* In protocol version 2.0, the data collection is identical, except that hospital re-admissions and deaths are collected through Month 12 only.

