## Appendix D. Schedule of Assessments

**Table D-1. Schedule of Assessments (protocol version 5.1, Appendix B).\***

	Screen or Day 0	Day 0	Follow-up Study Day; shaded columns denote in-person visits															
Day	-1/0 	0	1	2	3	4	5	6	7	14	28	42	60	75	90	6M	12M	18M
Acceptable deviation from day	0	0	0	0	0	0	0	0	+1	+2	+3	+3	+5	+5	+10	±14	±14	±14
ELIGIBILITY & BASELINE DATA																		
Informed consent	X																	
Baseline medical (incl. duration of COVID-19) and social history	X																	
Baseline medications	X																	
Symptom-directed physical exam by the clinical team	X																	
Review SARS-CoV-2 test results	X																	
Local laboratory testing	X							X										
Urine pregnancy test or other documentation of pregnancy status	X																	
STUDY INTERVENTION																		
Randomization		X																
Study Drug/Placebo Administration		X																
Assess infusion completion and adverse reactions		X																
STUDY PROCEDURES																		
Clinical assessment for pulmonary ordinal outcome	X	X	X	X	X	X	X	X	X	X	X							
Clinical assessment for pulmonary+ ordinal outcome	X	X	X	X	X	X	X	X	X									
Vital signs for NEW score assessment	X																	
Respiratory function scale assessment	X																	
Hospitalization status				X		X		X	X	X		X		X	X	X	X	X
Changes in residence/facility											X	X	X	X	X	X		
Interim medical history									X	X	X		X		X			
Interim medications						X				X								
Clinical AEs of any grade on days indicated		X	X	X	X	X	X	X	X	X	X							
Clinical AEs reaching grade 3 or 4 severity through Day 28										X	X							
Research sample storage (plasma and serum) 		X	X		X		X				X				X			
Midturbinate swab for central SARS-CoV-2 viral load testing 		X																
SAEs and unanticipated problems																		
Deaths																		
Hospitalization Summary																		
Hospital Readmissions																		

 Screening must be performed within 24 hours of randomization.

 Blood draw and swab collection in some cases can be obtained after randomization but before the infusion. If it is not possible to do an in-person on Day 3 or Day 5, the blood draws may be done one day earlier or one day later (but the participant should be telephoned to record the clinical data on the indicated study day).

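### MP0420: the planned rash count merges closely sampled early rash with the sparsely sampled delayed window in which the hypersensitivity signal arose, and should be split by onset day

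*SAP*

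**What the plan says.** SAP Appendix G (Hypersensitivity Events of Special Interest) explains the signal: in a study of healthy volunteers, three participants "developed non-serious (mild to moderate) rash and joint/body pain 10 to 20 days after the single subcutaneous infusion". It adds that "A total of 8 participants received the 400 mg dose in this study". For the trial itself, on 7 December 2021 "all participants for whom rash adverse events had been reported through Day 28 were identified", and sites completed a form for each such event. Eleven participants were found, arms pooled. The plan is a number and percentage with rash by arm, the same for rash accompanied by muscle, joint or general aches, a line listing, and rash as a separate component in a supplemental analysis of the Day 28 composite. No test is planned on rash alone.

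The underlying collection is set out in three places:

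- Section 7 has grade 1-4 clinical events reported at baseline, then "Day 0 after the infusion, Days 1-7, and on Days 14 and 28". It also says: "In addition to any grade AEs through Day 7, grade 3 and 4 clinical AEs are being reported through Day 28".
- Table C-1, footnote 1, gives a look-back rule for grade 3 and 4 events: "those occurring between Days 8 and 14 are reported at the Day 14 visit, and those occurring between Days 15 and 28" go to the Day 28 visit. No such rule is given for grades 1 and 2.
- Table D-1 has a row "Clinical AEs of any grade on days indicated", marked for Days 0-7, 14 and 28, and a separate row for events reaching grade 3 or 4 through Day 28.

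**The concern.** The reaction that prompted the analysis is below grade 3, and its onset falls mostly between the two any-grade contacts after Day 7. A mild rash that starts on Day 16 and clears by Day 24 has no stated route into the table, while a mild rash on Day 2 does. A single count through Day 28 adds the two kinds together. Early rash, which may be infusion-related or background, is well captured and may dominate the figure; the delayed reaction is the part captured least well. Onset day is not among the items named for the line listing, so a reader could not separate them from the planned output.

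At stake is how a low or balanced count is read. It could be taken as evidence that the volunteer reaction does not occur in patients, when the count may say little about the delayed window. The supplemental Day 28 composite has the same weakness: rash would stand beside components collected continuously.

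**Working it through.** The documents give no capture rate for rash, so there is no figure to reproduce.

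**Inputs from the SAP.** Onset 10-20 days after dosing (Appendix G). Any-grade contacts after Day 7 on Days 14 and 28, with windows of +2 and +3 days (Table D-1). Eleven participants with rash among 485 infused (Appendix G).

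**Assumptions.** Rash duration *d* is not given, so it is varied. Onset *t* is uniform over Days 10 to 20. A grade 1-2 rash is recorded only if it is present at a contact.

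**Formula.** A rash is recorded at a contact on day *v* if t ≤ v ≤ t + d. For contacts on Days 14 and 28:

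- Present on Day 14: t between max(10, 14 − d) and 14, a length of min(d, 4).
- Present on Day 28: t between 28 − d and 20, a length of max(0, d − 8).
- For d ≤ 14 the two ranges do not overlap, so share missed = 1 − [min(d, 4) + max(0, d − 8)] / 10.

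Examples: d = 3 gives 1 − 3/10 = 70%; d = 5 gives 1 − 4/10 = 60%; d = 10 gives 1 − (4 + 2)/10 = 40%; d = 14 gives 1 − (4 + 6)/10 = 0%.

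With both contacts at the end of their windows (Days 16 and 31), the share missed is 1 − [min(d, 6) + max(0, d − 11)] / 10 for d ≤ 15. A count in whole days (11 onset days, rash present on *d* consecutive days) is a check on the continuous model.

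| Rash duration | Missed, Days 14/28 | Same, whole-day count | Missed, Days 16/31 |
|---|---|---|---|
| 3 days | 70% | 8/11 = 73% | 70% |
| 5 days | 60% | 6/11 = 55% | 50% |
| 7 days | 60% | 6/11 = 55% | 40% |
| 9 days | 50% | 5/11 = 45% | 40% |
| 10 days | 40% | 4/11 = 36% | 40% |
| 12 days | 20% | 2/11 = 18% | 30% |
| 14 days | 0% | 0/11 = 0% | 10% |
| 15 days | 0% | 0% | 0% |

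**Sensitivity.**

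- Durations that vary exponentially (Days 14/28): 76% missed for a mean of 3 days, 65% for 5, 57% for 7, 47% for 10, 38% for 14. The fall to zero at 14 days depends on a fixed duration.
- Onset weighted towards Day 10, rash of 5 to 7 days: 36% missed; weighted towards Day 20: 84%.
- First contact on Day 14 and second on Day 31: 30% missed at 14 days, and none only from 31 − 14 = 17 days.

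**Not affected.** Rash on Days 0-7 is sampled daily, and grade 3-4 rash is carried back to the next contact. Observed rash is 11/485 = 2.3% of infused participants, all onset days and both arms together.

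**The case against.** The best counter-argument is that recording only what is present on the day is an inference. The SAP lists the days on which any-grade events are reported and nowhere forbids a look-back for grades 1 and 2. Table D-1 also schedules an interim medical history at the later contacts. The master protocol's safety section, the instruction manual and the MP0420 protocol appendix are not among the documents. This stands in part. A reader might infer that a mild rash between contacts was never asked about; the documents do not establish that. Still, it is the natural reading. Separate grade 3-4 rows to Day 28 would be redundant if the any-grade rows covered the gaps, and Section 7 ends its cumulative any-grade comparison at Day 7.

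Second, the analysis is descriptive, covers eleven participants, and comes with a line listing; leadership also asked investigators for greater vigilance. All true, and Appendix G does not call the percentage an incidence. But the request followed the October and November 2021 communications and changed no collection rule, and the case search took only rash already reported.

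Third, assignment is masked and both arms follow one schedule, so missed events do not by themselves create a false imbalance. That stands: the loss is one of sensitivity.

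A reader might also set 3 of 8 volunteers against 11 of 485 participants and conclude that events were lost. That comparison supports nothing: one group is healthy volunteers dosed subcutaneously, the other infused inpatients with active and placebo pooled.

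**Conclusion.** The point holds as a matter of how the table is built and labelled. One count through Day 28 combines two windows sampled at very different density, and the delayed window is the one the analysis was created to examine.

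The size of the loss is conditional. It concerns only grade 1-2 rash with delayed onset, and under uniform onset and contacts on schedule it runs from about 70% for a 3-day rash to nothing for a fixed duration of 14 days or more. It would be smaller if sites recorded events since the last contact. It is tempting to state flatly that the table misses half or more of the events it should count. The documents do not support that: they give no duration, the statement fails from 10 days upward in the base case, and early and grade 3-4 rashes are in the table. The 10-20 day window itself rests on three volunteers.

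**What to change.** In Appendix G, before unblinding:

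1. Tabulate rash, and rash with muscle or joint pain or general aches, by arm separately for onset on Days 0-7 and Days 8-28. Treat the Day 8-28 row as the delayed-hypersensitivity result.
2. Label that row as grade 1-2 events recorded at the Day 14 and Day 28 contacts plus all grade 3-4 events, not as complete incidence through Day 28. If sites did apply a look-back for grades 1-2, state the rule and adjust the label.
3. Add onset day to the line listing.
4. Apply the same split to the rash component of the supplemental Day 28 composite.

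The cost is a few lines of SAP text and one table split; Section 1.1 already provides for updates before unblinding. If onset day is not on the existing form, it needs a query for eleven participants. The downside is small cells, with eleven participants over two arms and two windows.

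A masked query to sites about unreported rash on Days 8-28 is optional. It would address the gap itself, but adds site work for up to 485 participants and relies on records or recall of a transient mild event.

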### **Subgroup Analyses**

In addition to the subgroup analyses described in section 9, those described in section E-7 (vaccine and immunosuppressive status) and E-8 (viral strain) of Appendix E will be carried out for MP0420 for the outcomes listed in section 9.

## Appendix H. List of Acronyms

ACTIV	Accelerating COVID-19 Therapeutic Interventions and Vaccines
ACTT	Adaptive COVID-19 Treatment Trial
ADE	Antibody-dependent enhancement
AE	Adverse event
Anti-N	Anti-nucleoprotein
ARDS	Acute respiratory distress syndrome
CHF	Congestive heart failure
CI	Confidence interval
CIF	Cumulative incidence curve
CMH	Cochran-Mantel-Haenszel [test]
COVID-19	Coronavirus-Induced Disease 2019
CVA	Cerebrovascular accident
DSMB	Data and Safety Monitoring Board
ECMO	Extracorporeal membrane oxygenation
EU	European Union
FDA	Food and Drug Administration (US)
GCP	Good Clinical Practice
GDPR	General Data Protection Regulation
GEE	Generalized estimating equations
GMT	Geometric mean titer
HR	Hazard ratio
ICC	International Coordinating Center
ICH	International Council for Harmonisation of Technical Requirements for Pharmaceuticals for Human Use
ICU	Intensive care unit
IgG	Immunoglobulin G
IL-1	Interleukin 1
IL-6	Interleukin 6
INSIGHT	International Network for Strategic Initiatives in Global HIV Trials
IQR	Interquartile range
IRB	Institutional Review Board
ITT	Intention-to-treat
IV	Intravenous
mAb	Monoclonal antibody
MedDRA	Medical Dictionary for Regulatory Activities
MI	Myocardial infarction
mITT	modified intention-to-treat
mL	Milliliter
nAb	Neutralizing antibody, here measured by a GenScript assay
NEW	National Early Warning [score]
NIAID	National Institute of Allergy and Infectious Diseases, NIH (US)
NIH	National Institutes of Health (US)
NIHSS	National Institutes of Health Stroke Scale/Score
NYHA	New York Heart Association
nMAb	Neutralizing Monoclonal Antibodies
OR	Odds ratio
PCR	Polymerase chain reaction

PIM	Protocol Instruction Manual
PT	Preferred term
PSEE	Protocol-specified exempt (serious) events
RNA	Ribonucleic acid
RR	Rate ratio
RRR	Recovery rate ratio
SAE	Serious adverse event
SARS-CoV-1	Severe acute respiratory syndrome coronavirus 1
SARS-CoV-2	Severe acute respiratory syndrome coronavirus 2
SAP	Statistical analysis plan
sHR	Sub-distribution hazard ratio; subhazard ratio
SOC	Standard of care
SUSAR	Suspected unexpected serious adverse reaction
TOC	Trial oversight committee
UMN	University of Minnesota
UP	Unanticipated problem
U.S.	United States of America
WHO	World Health Organization
